#### 9.7.1.1.2 SECONDARY ENDPOINTS

- Proportion of subjects who achieve seizure free status for POS, SGS, and PGTCS during the Maintenance Period.
- Proportion of subjects who achieve 3-month seizure-free status for POS, SGS, and PGTCS.
- Proportion of subjects who achieve 6-month seizure-free status for POS, SGS, and PGTCS.
- Proportion of subjects who receive perampanel as a 1st adjunctive therapy who are able to convert to perampanel monotherapy
- Safety and tolerability of perampanel administered as monotherapy or 1st adjunctive therapy in adolescents and adults

#### 9.7.1.1.3 EXPLORATORY ENDPOINTS

- 50% responder rate in total POS, SGS, and PGTCS; 50% responders are defined as subjects who have at least a 50% reduction in seizure frequency relative to baseline (in subjects with sufficient baseline seizure frequency data)
- 75% responder rate in total POS, SGS, and PGTCS; 75% responders are defined as subjects who have at least a 75% reduction in seizure frequency relative to baseline (in subjects with sufficient baseline seizure frequency data)
- Median percent change in total POS, SGS, and PGTCS frequency in the Titration and Maintenance Periods relative to baseline (in subjects with sufficient baseline seizure frequency data)
- Proportion of subjects with no/mild/clear cognitive impairment relative to baseline using the EpiTrack total score
- Change in subjective sleep quality at the end of the Maintenance Period relative to baseline using the PSQI

- Change in quality of life at the end of the Maintenance Period relative to baseline using the QOLIE-31

#### 9.7.1.2 Definitions of Analysis Sets

The Safety Analysis Set (SAS) is the group of subjects who received at least 1 dose of study drug and had at least 1 postdose safety assessment.

The Full Analysis Set (FAS) is the group of subjects who received at least 1 dose of study drug and had at least 1 postdose seizure measurement.

#### 9.7.1.3 Subject Disposition

The disposition of all subjects will be summarized. Subject disposition tables will include the number (percent) of subjects who will be:

- Included in each analysis population
- Discontinued from the study early, summarized by reason for discontinuation
- Screened and the number (percent) who fail screening will also be summarized

#### 9.7.1.4 Demographic/Baseline Characteristics

Demographic and other baseline characteristics (eg, age, sex) for the SAS will be summarized using descriptive statistics. Continuous variables will be summarized using mean, SD, median, minimum, maximum and categorical variables will be summarized using number and percentages of subjects.

#### 9.7.1.5 Prior and Concomitant Therapy

The number (percentage) of subjects who took prior and concomitant medications will be summarized on the SAS by Anatomical Therapeutic Chemical class. Prior medication is defined as any medication that stopped before the 1st dose of study drug. Concomitant medication is defined as any medication that (1) started before the 1st dose of study drug and was continuing at the time of the 1st dose of study drug, or (2) started on or after the date of the study drug until the last dose of study drug.

#### 9.7.1.6 Efficacy Analyses

This is a study without a control arm. Therefore, formal hypothetical inferences are not necessary, and only descriptive statistics will be performed, as shown below:

For percent change in seizure frequency endpoints:

- Mean, standard deviation, median (95% CIs), minimum, and maximum will be provided.

For responder rate endpoints:

- Number of responders
- Responder rate and its 95% CI

The details for the analyses will be described in the statistical analysis plan.

#### **9.7.1.6.1 PRIMARY EFFICACY ANALYSIS**

The SAS will be used to summarize retention rate. The retention rate, defined as the proportion of patients remaining on perampanel treatment at 3, 6, 9, and 12 months after initiation of treatment, will be summarized.

The number and percentage of subjects remaining on treatment at each time point and 95% CIs will be summarized.

#### **9.7.1.6.2 SECONDARY EFFICACY ANALYSES**

The FAS will be used to summarize seizure data.

#### **9.7.1.6.3 EXPLORATORY EFFICACY ANALYSES**

Analyses of exploratory efficacy endpoints will be performed in the subset of the FAS with sufficient baseline seizure frequency. All summaries will be produced by seizure type (POS, SGS, and PGTCS).

#### **9.7.1.7 Pharmacokinetic, Pharmacodynamic, Pharmacogenomic, and Other Biomarker Analyses**

##### **9.7.1.7.1 PHARMACOKINETIC ANALYSES**

Not applicable.

##### **9.7.1.7.2 PHARMACODYNAMIC ANALYSES**

Not applicable.

##### **9.7.1.7.3 PHARMACOGENOMIC ANALYSES**

Variation in exposure of perampanel, baseline levels and changes in clinical measurements (eg, efficacy or other safety parameters such as labs), or occurrence of AEs may be evaluated by testing for association of genetic variants with these measurements or traits. Details of any pharmacogenomic analyses will be described and reported separately.

#### **9.7.1.8 Safety Analyses**

The SAS will be used to summarize all safety variables. Safety data will be summarized using descriptive statistics (eg, n, mean, standard deviation, median, minimum, maximum for continuous variables; n [percentage] for categorical variables). Safety summaries will

include treatment-emergent adverse events (TEAEs) including SAEs and TEAEs resulting in discontinuation of perampanel.

#### **9.7.1.8.1 EXTENT OF EXPOSURE**

The extent of exposure to the study drug during the Titration and the Maintenance Period will be summarized descriptively.

#### **9.7.1.8.2 ADVERSE EVENTS**

The AE verbatim descriptions (investigator terms from the eCRF) will be classified into standardized medical terminology using the Medical Dictionary for Regulatory Activities (MedDRA). AEs will be coded to the MedDRA (most recent version) lower level term closest to the verbatim term. The linked MedDRA preferred term (PT) and primary system organ class (SOC) are also captured in the database.

Only those AEs that are treatment-emergent will be included in summary tables. All AEs, treatment-emergent or otherwise, will be presented in subject data listings.

The incidence of TEAEs will be reported as the number (percentage) of subjects with TEAEs by SOC and PT. A subject will be counted only once within an SOC and PT, even if the subject experienced more than 1 TEAE within a specific SOC and PT. The number (percentage) of subjects with TEAEs will also be summarized by maximum severity (mild, moderate, or severe).

The number (percentage) of subjects with TEAEs will also be summarized by relationship to study drug (Yes [related] and No [not related]).

The number (percentage) of patients with TEAEs leading to death will be summarized by MedDRA, SOC, and PT. A patient data listing of all TEAEs leading to death will be provided.

The number (percentage) of patients with treatment-emergent SAEs and AEs leading to discontinuation will be summarized by MedDRA, SOC, and PT. A patient data listing of all SAEs will be provided.

#### **9.7.1.8.3 COGNITION, DEPRESSION, AND SUICIDALITY**

Cognitive function in subjects 6 years of age and older will be evaluated using EpiTrack. It will be administered at Visits 2, 4, and 7 (Weeks 0, 13, and 52, respectively). Summaries of the proportion of subjects with no/mild/clear cognitive impairment and shifts between these categories from baseline to end of treatment will be produced. The BDI-II will be used to assess depression. Suicidality will be assessed using the C-SSRS and summaries will include the incidence of suicidal behavior and suicidal ideation. The C-SSRS will be administered to patients 6 years of age and older. Subjects under 6 years of age will be clinically monitored for suicidality. (revised per Amendment 01)

#### **9.7.1.8.4 VITAL SIGNS AND WEIGHT MEASUREMENTS**

Vital signs and body weight will be summarized. Descriptive statistics for vital signs parameters, weight and changes from baseline will be presented by visit.

#### **9.7.2 Determination of Sample Size**

The efficacy of perampanel as monotherapy and 1st adjunctive therapy for POS and PGTCS is to be evaluated. The primary endpoint is retention rate. There is no statistical hypothesis to be tested in this study.

The study is to enroll approximately 125 subjects. (revised per Amendment 01)

#### **9.7.3 Interim Analysis**

Interim analyses will be conducted at various intervals, depending on the number of accrued subjects.

#### **9.7.4 Other Statistical/Analytical Issues**

Not applicable.

---

## **11 PROCEDURES AND INSTRUCTIONS (ADMINISTRATIVE PROCEDURES)**

### **11.1 Changes to the Protocol**

Any change to the protocol requires a written protocol amendment or administrative change that must be approved by the sponsor before implementation. Amendments specifically affecting the safety of subjects, the scope of the investigation, or the scientific quality of the study require submission to health or regulatory authorities as well as additional approval by the applicable IRBs/IECs. These requirements should in no way prevent any immediate action from being taken by the investigator, or by the sponsor, in the interest of preserving the safety of all subjects included in the study. If the investigator determines that an immediate change to or deviation from the protocol is necessary for safety reasons to eliminate an immediate hazard to the subjects, the sponsor's medical monitor and the IRB/IEC for the site must be notified immediately. The sponsor must notify the health or regulatory authority as required per local regulations.

Protocol amendments that affect only administrative aspects of the study may not require submission to health or regulatory authority or the IRB/IEC, but the health or regulatory authority and IRB/IEC should be kept informed of such changes as required by local regulations. In these cases, the sponsor may be required to send a letter to the IRB/IEC and the Competent Authorities detailing such changes.

### **11.2 Adherence to the Protocol**

The investigator will conduct the study in strict accordance with the protocol (refer to ICH E6, Section 4.5).

### **11.3 Monitoring Procedures**

The sponsor's/CRO's CRA will maintain contact with the investigator and designated staff by telephone, letter, or email between study visits. Monitoring visits to each site will be conducted by the assigned CRA as described in the monitoring plan. The investigator will allow the CRA to inspect the clinical, laboratory, and pharmacy facilities to assure compliance with GCP and local regulatory requirements. The eCRFs and subject's corresponding original medical records (source documents) are to be fully available for review by the sponsor's representatives at regular intervals. These reviews verify adherence to study protocol and data accuracy in accordance with local regulations. All records at the site are subject to inspection by the local auditing agency and to IRB/IEC review.

In accordance with ICH E6, Section 1.52, source documents include, but are not limited to, the following:

- Clinic, office, or hospital charts
- Copies or transcribed health care provider notes that have been certified for accuracy after production

- Recorded data from automated instruments such as an interactive voice response system, x-rays, and other imaging reports (eg, sonograms, computed tomography scans, magnetic resonance images, radioactive images, electrocardiographs, rhythm strips, EEG, polysomnographs, pulmonary function tests) regardless of how these images are stored, including microfiche and photographic negatives
- Pain, quality of life, or medical history questionnaires completed by subjects
- Records of telephone contacts
- Diaries or evaluation checklists
- Drug distribution and accountability logs maintained in pharmacies or by research personnel
- Laboratory results and other laboratory test outputs (eg, urine pregnancy test result documentation and urine dip-sticks)
- Correspondence regarding a study subject's treatment between physicians or memoranda sent to the IRBs/IECs
- eCRF components (eg, questionnaires) that are completed directly by subjects and serve as their own source

#### **11.4 Recording of Data**

An eCRF is required and must be completed for each subject by qualified and authorized personnel. All data on the eCRF must reflect the corresponding source document, except when a section of the eCRF itself is used as the source document. Any correction to entries made on the eCRF must be documented in a valid audit trail where the correction is dated, the individual making the correction is identified, the reason for the change is stated, and the original data are not obscured. Only data required by the protocol for the purposes of the study should be collected.

The investigator must sign each eCRF. The investigator will report the eCRFs to the sponsor and retain a copy of the eCRFs.

#### **11.5 Identification of Source Data**

All data to be recorded on the eCRF must reflect the corresponding source documents.

#### **11.6 Retention of Records**

The circumstances of completion or termination of the study notwithstanding, the investigator is responsible for retaining all study documents, including but not limited to the protocol, copies of eCRFs, the Investigator's Brochure, and regulatory agency registration documents (eg, ICFs, and IRB/IEC correspondence). The site should plan to retain study documents, as directed by the sponsor, for at least 2 years after the last approval of a marketing application in an ICH region and until there are no pending or contemplated

marketing applications in an ICH region or at least 3 years have elapsed since the formal discontinuation of clinical development of the investigational product.

It is requested that at the completion of the required retention period, or should the investigator retire or relocate, the investigator contact the sponsor, allowing the sponsor the option of the period of retaining the study records.

### **11.7 Auditing Procedures and Inspection**

In addition to routine monitoring procedures, the sponsor's Clinical Quality Assurance department conducts audits of clinical research activities in accordance with the sponsor's standard operating procedures to evaluate compliance with the principles of ICH GCP and all applicable local regulations. If a government regulatory authority requests an inspection during the study or after its completion, the investigator must inform the sponsor immediately.

### **11.8 Handling of Study Drug**

All study drug will be supplied to the PI (or a designated pharmacist) by the sponsor. Drug supplies must be kept in an appropriate secure area (eg, locked cabinet) and stored according to the conditions specified on the drug labels. The investigator (or a designated pharmacist) must maintain an accurate record of the shipment and dispensing of the study drug in a drug accountability ledger, a copy of which must be given to the sponsor at the end of the study. An accurate record of the date and amount of study drug dispensed to each subject must be available for inspection at any time. The CRA will visit the site and review these documents along with all other study conduct documents at appropriate intervals once study drug has been received by the site.

All drug supplies are to be used only for this study and not for any other purpose. The investigator (or site personnel) must not destroy any drug labels or any partly used or unused drug supply before approval to do so by the sponsor. At the conclusion of the study and as appropriate during the study, the investigator (or a designated pharmacist) will return all used and unused drug containers, drug labels, and a copy of the completed drug disposition form to the sponsor's CRA or, when approval is given by the sponsor, will destroy supplies and containers at the site.

### **11.9 Publication of Results**

All manuscripts, abstracts, or other modes of presentation arising from the results of the study must be reviewed and approved in writing by the sponsor in advance of submission pursuant to the terms and conditions set forth in the executed Clinical Trial Agreement between the sponsor/CRO and the institution/investigator. The review is aimed at protecting the sponsor's proprietary information existing either at the date of the commencement of the study or generated during the study.

The detailed obligations regarding the publication of any data, material results, or other information generated or created in relation to the study shall be set out in the agreement between each investigator and the sponsor or CRO, as appropriate.

### **11.11 Discontinuation of Study**

The sponsor reserves the right to discontinue the study for medical reasons or any other reason at any time. If a study is prematurely terminated or suspended, the sponsor will promptly inform the investigators/institutions and regulatory authorities of the termination or suspension and the reason(s) for the termination or suspension. The IRB/IEC will also be informed promptly and provided the reason(s) for the termination or suspension by the sponsor or by the investigator/institution, as specified by the applicable regulatory requirement(s).

The investigator reserves the right to discontinue the study should his/her judgment so dictate. If the investigator terminates or suspends a study without prior agreement of the sponsor, the investigator should inform the institution where applicable, and the investigator/institution should promptly inform the sponsor and the IRB/IEC and provide the sponsor and the IRB/IEC with a detailed written explanation of the termination or suspension. Study records must be retained as noted above.

### **11.12 Subject Insurance and Indemnity**

The sponsor will provide insurance for any subjects participating in the study in accordance with all applicable laws and regulations.

## **12 APPENDICES**

Not applicable.

## 2 LIST OF ABBREVIATIONS AND DEFINITIONS OF TERMS

Abbreviation	Term
AE	adverse event
AED	antiepileptic drug
ATC	anatomical therapeutic class
BDI-II	Beck depression inventory-II
BP	blood pressure
CI	confidence interval
CRF	case report form
C-SSRS	Columbia-Suicide Severity Rating Scale
DMC	Data Monitoring Committee
EOT	end of treatment
FAS	Full Analysis Set
LOCF	last observation carried forward
MedDRA	Medical Dictionary for Regulatory Activities
PGTCS	primary generalized tonic-clonic Seizures
POS	partial-onset seizures
PSQI	Pittsburgh Sleep Quality Index
PT	preferred term
QOLIE-31	Quality of Life in Epilepsy Inventory-31
SAE	serious adverse event
SAP	statistical analysis plan
SAS	Safety Analysis Set
SD	Standard deviation
SGS	Secondarily Generalized Seizures
SOC	system organ class
TEAE	treatment-emergent adverse event
TLG	tables, listings, and graphs
WHO DD	World Health Organization drug dictionary

### 3 INTRODUCTION

The purpose of this statistical analysis plan (SAP) is to describe the procedures and the statistical methods that will be used to analyze and report results for the Eisai Protocol E2007-G000-410.

#### 3.1 Study Objectives

##### 3.1.1 Primary Objective

To assess the retention rate of perampanel when given as monotherapy or 1st adjunctive therapy in subjects with partial-onset seizures (POS) or primary generalized tonic-clonic seizures (PGTCS).

##### 3.1.2 Secondary Objectives

- To evaluate the efficacy of perampanel when given as monotherapy or 1st adjunctive therapy in subjects with POS or PGTCS as measured by seizure freedom
- To assess the proportion of subjects with POS or PGTCS that are able to convert from 1st adjunctive therapy to perampanel monotherapy
- To assess the safety of perampanel as initial monotherapy or 1st adjunctive therapy in subjects with POS or PGTCS
- To assess dosing and titration of perampanel when administered as initial monotherapy or 1st adjunctive therapy in subjects with POS or PGTCS

##### 3.1.3 Exploratory Objectives

- To evaluate the efficacy of perampanel in subjects with POS or PGTCS as measured by responder rates (50% and 75%, in subjects who have sufficient baseline seizure frequency data available)
- To evaluate the efficacy of perampanel in subjects with POS or PGTCS as measured by median percent reduction in seizure frequency (in subjects who have sufficient baseline seizure frequency data available)
- To assess cognition, including the impact of depression, in subjects with POS or PGTCS administered perampanel as monotherapy or as 1st adjunctive therapy.
- To assess subjective sleep quality in subjects with POS or PGTCS administered perampanel as monotherapy or as 1st adjunctive therapy
- To assess quality of life in subjects with POS or PGTCS administered perampanel as monotherapy or as 1st adjunctive therapy

[figure not shown]
### 3.2 Overall Study Design and Plan

This is a multi-center, open-label, Phase 4 study. Subjects who met all of the inclusion and none of the exclusion criteria will receive perampanel. Baseline seizure counts (frequency) data will be collected by subjects or guardian/legally authorized representative, retrospectively (for history prior to screening) and prospectively as needed (during baseline). The study consists of 4 periods: a Screening Period (to start no earlier than 6 weeks before the 1st dose of study drug), a Titration Period (13 weeks), a Maintenance Period (39 weeks), and a Follow-up Period (4 weeks). The study duration for each subject is expected to be approximately 1 year in total.

Study subjects includes the following:

- Subjects who have been diagnosed with POS or PGTCS but have not previously received treatment with an antiepileptic drug (AED) or are receiving monotherapy treatment (no history of AED polytherapy) and wish to switch to another monotherapy treatment; or
- Subjects who are receiving treatment with a single AED administered at a stable dose for at least 8 weeks before Visit 2 (Week 0) and needs additional AED treatment; subjects should not have previously received adjunctive AED therapy.

An overview of the study design is presented below.

#### 4 DETERMINATION OF SAMPLE SIZE

The efficacy of perampanel as monotherapy and 1st adjunctive therapy for POS and PGTCs is to be evaluated. The primary endpoint is retention rate. The study is planned to enroll approximately 125 subjects. This sample size is considered adequate for an open-label Phase 4 study where there is no statistical hypothesis to be tested.

#### 5 STATISTICAL METHODS

All descriptive statistics for continuous variables will be reported using mean, standard deviation (SD), median, minimum, and maximum. Categorical variables will be summarized as number (percentage) of subjects.

All summaries of seizure-related efficacy endpoints will be produced by seizure type (POS, secondarily generalized seizures [SGS], and PGTCs) and overall. Summaries of retention rate and safety data will be produced by seizure type (POS, SGS, and PGTCs) and overall.

## 5.1 Study Endpoints

### 5.1.1 Primary Endpoint

The primary endpoint is retention rate, defined as the proportion of subjects remaining on perampanel at the specified time points: 3, 6, 9, and 12 months after initiation of treatment.

### 5.1.2 Secondary Endpoints

- Proportion of subjects who achieve seizure free status for POS, SGS, and PGTCs during the Maintenance Period.
- Proportion of subjects who achieve 3-month seizure-free status for POS, SGS, and PGTCs.
- Proportion of subjects who achieve 6-month seizure-free status for POS, SGS, and PGTCs.
- Proportion of subjects who receive perampanel as a 1st adjunctive therapy who are able to convert to perampanel monotherapy
- Safety and tolerability of perampanel administered as monotherapy or 1st adjunctive therapy in adolescents and adults
- Maximum and last dose during the titration period and the maintenance period

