### 9.3.1 Inclusion Criteria

Subjects must meet all of the following criteria to be included in this study:

1. Subjects will be male or female and no younger than 4 years of age and be able to swallow perampanel tablets. (revised per Amendment 01)
2. Subjects must have a diagnosis of epilepsy with POS with or without SGS, or with PGTCS. Either of the following must have occurred to support an epilepsy diagnosis: (revised per Amendment 01)
  - a. At least 2 unprovoked (or reflex) seizures occurring greater than 24 hours apart

- b. 1 unprovoked (or reflex) seizure with EEG evidence of seizures
3. Subjects who receive perampanel as a 1st adjunctive therapy must currently have been treated with stable doses of monotherapy with an AED for 8 weeks prior to Visit 2 (Week 0), have not previously received adjunctive AED treatment, and must, in the investigator's judgement, be in need of initial adjunctive therapy after failure to control seizures with AED monotherapy, at the optimal dose and duration. (revised per Amendment 01)
4. Subjects who receive perampanel as monotherapy, who were newly diagnosed (treatment naïve), following the defined diagnosis of epilepsy. (revised per Amendment 01)
5. Subjects who are currently receiving monotherapy treatment may receive perampanel as monotherapy if, in the investigator's judgment, the subject may benefit from a change in monotherapy treatment. Subjects must not have previously received adjunctive AED treatment.
6. If antidepressants or antianxiety drugs are used, subjects must be on a stable dose regimen of these drugs during the 8 weeks before Visit 2 (Week 0).

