## 5.2 Study Subjects

### 5.2.1 Definitions of Analysis Sets

The Safety Analysis Set (SAS) is the group of subjects who received at least 1 dose of study drug and had at least 1 postdose safety assessment.

The Full Analysis Set (FAS) is the group of subjects who received at least 1 dose of study drug and had at least 1 postdose seizure measurement.

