### 5.3.4 Examination of Subgroups

All summaries of seizure-related efficacy endpoints will be produced by seizure type (POS, SGS, and PGTCS) and overall. Summaries of retention rate and safety data will be produced by seizure type (POS, SGS, and PGTCS) and overall. All summaries of retention rate and seizure-related efficacy endpoints will also be produced by sex and age group (<12, 12-<=18, 18-<=65, >65).

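### The secondary safety endpoint names only adolescents and adults although the trial enrols from age 4, and no planned safety summary shows children separately

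*SAP*

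**What the plan says.** - **Endpoint.** SAP 5.1.2 lists as a secondary endpoint: "Safety and tolerability of perampanel administered as monotherapy or 1st adjunctive therapy in adolescents and adults". Protocol Section 2 (Secondary Endpoints) and Protocol 9.7.1.1.2 use the same words.
- **Eligibility.** Protocol 9.3.1, item 1, admits subjects "no younger than 4 years of age and be able to swallow perampanel tablets".
- **Objective.** SAP 3.1.2 (and Protocol 8.2) states the matching objective without an age limit: "To assess the safety of perampanel as initial monotherapy or 1st adjunctive therapy in subjects with POS or PGTCS".
- **Analysis set.** SAP 5.2.1 defines the Safety Analysis Set by dosing and a later safety evaluation, with no age criterion. SAP 5.6 uses this set for every safety variable.
- **Safety subgroups.** SAP 5.3.4: "Summaries of retention rate and safety data will be produced by seizure type (POS, SGS, and PGTCS) and overall".
- **Age subgroups.** The next sentence of SAP 5.3.4 reads: "All summaries of retention rate and seizure-related efficacy endpoints will also be produced by sex and age group (<12, 12-<=18, 18-<=65, >65"). Safety is not named.
- **Listings.** SAP 5.6.2 puts all adverse events into subject data listings. It adds listings of serious events, events leading to death and events leading to discontinuation.
- **Numbers.** SAP Section 4 plans about 125 subjects. SAP Section 7 says that enrolment stopped before that number was reached and that there will be too few subjects for 95% confidence intervals. Neither document gives the number of children.

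**The concern.** An endpoint should name the population in which it is measured. Read literally, this one leaves out the youngest subjects, while the objective it serves and the tables that report it include them. A reader of the study report could not tell whether the safety endpoint was met by the all-ages tables or needed a restricted analysis that nobody planned.

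The second part concerns what the report will show. The plan gives retention and seizure results for subjects under 12, with no matching adverse event summary for the same group. Protocol 7.2 says that there is little clinical-study information on perampanel as monotherapy. Protocol 9.4.4 gives the approval for PGTCS as starting at age 12, while this study admits subjects with PGTCS from age 4. Safety in the younger subjects is something that readers will look for, and a pooled table dominated by older subjects would say little about it.

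**Working it through.** The plan states no figure on this point, so the main check sets the texts side by side.

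| Element | Place | Ages covered |
|---|---|---|
| Safety objective | SAP 3.1.2; Protocol 8.2 | No limit |
| Eligibility | Protocol 9.3.1 | 4 and older |
| Safety endpoint | SAP 5.1.2; Protocol Section 2 and 9.7.1.1.2 | Adolescents and adults |
| Safety Analysis Set | SAP 5.2.1, used in 5.6 | No limit |
| Safety subgroups | SAP 5.3.4 | Seizure type and overall; no age split |
| Retention and seizure subgroups | SAP 5.3.4 | Also by sex and age, with an under-12 group |

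1. The endpoint is the only one of these elements restricted to adolescents and adults, so it is out of line with the objective above it and the analysis below it.
2. SAP 5.6 adds no age split. C-SSRS and EpiTrack start at age 6. EpiTrack Junior has its own scoring in SAP 13.1, but no separate summary of it is stated, and its range of 6 to 16 years mixes children with adolescents.
3. The age groups overlap: both the second and the third contain age 18. If they were extended to safety unchanged, an 18-year-old could be counted twice.

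**Illustration of masking.** All inputs except 125 are assumptions. Let n be the number of children, and let the event rate be 30% in them and 10% in the others.

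Pooled rate = (n × 0.30 + (125 − n) × 0.10) / 125

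- 5% children, n = 6: (1.8 + 11.9) / 125 = 0.1096, about 11.0%
- 10% children, n = 12: (3.6 + 11.3) / 125 = 0.1192, about 11.9%
- 20% children, n = 25: (7.5 + 10.0) / 125 = 0.140, or 14.0%

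**What a separate count could show.** If the rate in children were 10%, the chance of at least one event among them is 1 − 0.9^n. If no event were seen, the one-sided 95% upper bound on their rate is 1 − 0.05^(1/n).

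| n | Chance of at least one event | Upper bound with zero events |
|---|---|---|
| 6 | 47% | 39% |
| 12 | 72% | 22% |
| 25 | 93% | 11% |

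These figures use the full planned 125. Enrolment fell short of that, so at the same shares the numbers of children would be smaller and the bounds wider.

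**The case against.** The strongest reply is that this is a label that was not updated, with no effect on any planned number. Amendment 01 changed the minimum age, and the revision history does not list the endpoint sections among those affected by that change. No analysis rule uses the phrase, and neither document defines an adolescent. This explains the slip and shows that no existing table would change. It does not make the endpoint text correct, and SAP Section 7 records no intention to restrict safety by age.

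A reader might infer that children are left out of the safety analysis, or that no planned result shows anything about their safety. The documents do not support this. Every dosed child with a postdose safety assessment is in the Safety Analysis Set and its tables, and all adverse events are listed by subject. Retention under 12 is also planned, and Protocol 9.2.2 treats retention as reflecting both efficacy and safety. Retention is not adverse event data, however, and a listing is not a summary.

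It can also be said that splitting safety by seizure type only is a legitimate choice in an uncontrolled descriptive study, and that an under-12 table by system organ class and preferred term might hold only a few cells of one or two subjects. Both points have force. They favour simple counts or a listing over inference, but they do not explain why a group already defined for efficacy should have no safety counterpart.

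**Conclusion.** The endpoint population is wrong as written in all three places, because it does not match eligibility, the objective or the analysis set. Separately, no planned safety summary shows children on their own, although the SAP already defines an under-12 group and uses it for retention and seizure endpoints. The first part is an error of wording. The second is a gap that can be closed at almost no cost.

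How much the pooled tables could hide is unknown. The range of 11% to 14% rests on an assumed share of children, assumed event rates and the full planned enrolment. It shows that a threefold difference could be nearly invisible, not that one exists. Nor would a separate table settle the question: with 12 children and no events, a rate up to 22% would still be compatible with the data.

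**What to change.** 1. In SAP 5.1.2, define the safety endpoint for all enrolled subjects, aged 4 years and older. Align Protocol Section 2 and Protocol 9.7.1.1.2 or, since enrolment has ended, record the correction in SAP Section 7.
2. In SAP 5.3.4, assign age 18 to one group only.
3. Then extend the age groups to three summaries: treatment-emergent adverse events, serious adverse events, and treatment-emergent adverse events leading to discontinuation.
4. State that these are descriptive counts. If very few children were enrolled, replace the under-12 column with an under-12 listing.

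The cost is a few lines of text and three repeat tables on data already collected. The downside is that some cells may be sparse. Trial conduct does not change.
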